3.1 Study design

The study design will be an open cohort stepped wedge cluster randomized controlled trial (SW-CRT) in six central/provincial hospitals across Laos. SW-CRT is appropriate in the Lao context because it requires fewer sites than a parallel cluster trial, but has similar observational periods for reference and intervention phases. As the interventions will be delivered by one team travelling to each cluster in turn, implementing in stages will be more practical. In addition, all participating hospitals will have access to the novel interventions at the end of the study. Prescribers are allowed to move in and out of clusters during the trial.

3.2 Study sites

Six hospitals (two referral (200-450 beds) and four provincial hospitals (60-100 beds) have been purposively selected based on their capacity, location, previous participation in our PPS program with available hospital antimicrobial use and antimicrobial susceptibility data.

Mahosot Hospital (MS) has 450 beds and is a central referral hospital situated in Vientiane City in Laos (17°95'N 102°61'E, 268m above mean sea level). There are 968 staff, including 222 physicians,

414 nurses, 19 dentists, 46 pharmacists, 11 radiologists and 147 non-health worker staff. There are 18 in-patient wards and one main out-patient and small number of OPDs within in-patient wards.

Vientiane Provincial Hospital (VTP) has 100 beds. There are 211 staff, including 30 physicians, 99 nurses, 6 dentists and 9 pharmacists (data from 2018). There are six in-patient wards and one outpatient ward. The hospital is ~70km from Vientiane City (18°47'N 102° 48'E 497m above mean sea level).

[figure not shown]
Xiengkhuang Provincial Hospital (XK) has 150 beds. There are 305 staff, including 66 physicians, 117 nurses, 6 dentists and 24 pharmacists (data from 2019). There are 11 in-patient wards and one main out-patient units and a small number of OPDs within in-patient wards. It is in a broad valley in the northeast highlands (19° 27'N 103° 10'E, 1,150m above mean sea level).

Luang Namtha Provincial Hospital (LNT) has 50 beds. There are 117 staff, including 18 physicians, 36 nurses, 3 dentists and 10 pharmacists (data from 2018). There are 6 in-patient wards and OPDs within in-patient wards. It is in the highlands on the China and Myanmar borders in the far NW of Laos (21° 00'N 101° 24' E; 570m above mean sea level)

Savannakhet Provincial Hospital (SVK) has 200 beds. There are 293 staff, including 60 physicians, 139 nurses, 7 dentists and 13 pharmacists (data from 2019). There are 9 in-patient wards and one main out-patient and small number of OPDs within in-patient wards. It is located in the southern part of the country in the largest province in Laos (16° 55'N 104° 74'E; 726 m above mean sea level)

Salavan Provincial Hospital (SV) has 70 beds. There are 191 staff, including 30 physicians, 50 nurses, 3 dentists and 11 pharmacists (data from 2018). There are 7 in-patient wards and OPDs within in-patient wards outpatient. It is on the western slopes of Annamite mountains in southern Laos (15°43'N 106°25' E; 184m above mean sea level).

Figure 1. SW-CRCT study sites

3.3 Sample size and power calculation

A PPS of hospital antimicrobial use in four general hospitals in Laos in 2017 showed 13% compliance to Lao treatment guidelines (LOMWRU unpublished data) but previous guidelines did not contain much information on antibiotic prescribing, therefore reliable baseline data are lacking.

The sample size of 6 hospitals was estimated assuming 30% of antimicrobial prescription adherence with the paper-based prescribing guideline (reference), and assuming 0.05 intra-cluster correlation coefficient. This will have 80% of power of the test to be able to detect 15% minimum difference after introduction of the mobile phone app prescribing guidelines at 0.05 significant level.

This will be a 3-step trial with one baseline measurement after introduction of the paper-based prescribing guidelines. The outcomes will be measured every four months. These will give four outcomes measurements in total (excluding baseline measurement at start), until the trial

completes at month 16.

3.4 Randomization and blinding

Six participating hospitals have been divided into 3 pairs based on the geographical location and convenience for conducting the surveys. The first paired hospitals include two provincial hospitals from the north of Laos (Luang Namtha and Xiengkhuang), the second pair includes hospitals in the center (Mahosot Hospital-central referral hospital and Vientiane provincial hospital which is 80 km from the center of the capital to the north). The third pair includes two provincial hospitals from the south of Laos (Savannakhet and Salavan).

As there are only 3 orders to be assigned, clusters will be randomly assigned to one of three start dates using a simple random sampling, to have access to the study intervention. Three paired hospitals (LNT+XK, MS+VTP and SVK+SV) will be written on three different paper slips (similar paper size and paper texture). All slips will be folded to the same size and put in the non-transparent container, covered firmly and mixed well. A person who is not related to the study will be asked to pick up the paper slip one by one and read out to the PI and a co-investigator. Simple random sampling processes will be performed before the start of the project and the order of each paired hospital to intervention introduction will be recorded. At month 4 after the start of the project, the intervention will be introduced to the first selected paired hospital, then every four months each pair of hospitals will be rolled out from the reference phase to the intervention phase until all have started the intervention. This will give 1:1 ratio of intervention vs reference period of observation (figure 2). We will therefore be able to compare the effects of the reference and intervention over a reasonable period of time. Neither hospitals nor investigators will be blinded to the introduction of the intervention.

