Study duration	16 months (four months preintervention period and 4-month interval between each step (three steps))
Sample size and power calculation	The sample size of six hospitals was estimated assuming 30% antimicrobial prescription adherence with the paper-based prescribing guidelines (reference), and assuming 0.05 intra-cluster correlation coefficient. This will have 80% power to be able to detect a 15% minimum difference in adherence after introduction of the mobile phone app prescribing guidelines (intervention) at a 0.05 significance level.
Randomization and blinding	Simple random sampling will be used to select the order (step) of interventions implementation for a group of hospitals (two hospitals per group and one group per step). Neither hospitals nor investigators will be blinded to the timing of intervention.
Intervention	A MicroGuide antimicrobial prescribing guideline mobile phone application and

	AMS training
Reference	Paper-based antimicrobial prescribing guidelines
Outcomes/Primary endpoint	The proportion of antimicrobial prescriptions adherent with prescribing guidelines delivered by mobile phone app versus paper-based prescribing guidelines at month 16 (12 months' exposure in each group)
Secondary endpoints	
 1. Total antimicrobial defined daily doses (DDDs) prescribed in mobile phone app versus paper-based groups after 12 months' exposure in each group 2. Proportion of patients prescribed antimicrobials by the oral route in mobile phone app versus paper-based groups after 12 months' exposure in each group 3. AMS knowledge level of prescribers prescribed in mobile phone app versus paper-based groups after 12 months' exposure in each group 4. Prescriber satisfaction/acceptability of the prescribing guidelines in mobile phone app versus paper-based groups after 4 months' exposure in each group 5. Total costs of antimicrobials prescribed in mobile phone app versus paper-based groups after 12 months' exposure in each group 6. Proportion of patients admitted to hospital receiving an antimicrobial prescription before and after introduction of the paper-based prescribing guidelines; and the mobile phone app prescribing guidelines + AMS training after 12 months' exposure in each group
Outcome measurement	
 • Point prevalence surveys (PPS) of hospital antimicrobial use • Prescriber questionnaires • AMS knowledge surveys of prescribers

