- b. During the intervention period, prescribers in participating hospitals still have access to paper-based prescribing guidelines distributed at the start of the study. Mobile phone prescribing guidelines surveys (Appendix A11) will be used as a tool to access the use of the mobile phone app prescribing guidelines and the paper prescribing guidelines at the end of the study

Figure 2: Study procedures of SW-CRT on Evaluation of Lao-language antimicrobial use guidelines mobile app

	Study phase				
	Pre-study phase				
Hospital 6	PPS+Report	PPS+Report+Paper-based	PPS+Report+Paper-based	PPS+Report+Paper-based	PPS+Report+App+AMS
Hospital 5	PPS+Report	PPS+Report+Paper-based	PPS+Report+Paper-based	PPS+Report+Paper-based	PPS+Report+App+AMS
Hospital 4	PPS+Report	PPS+Report+Paper-based	PPS+Report+Paper-based	PPS+Report+App+AMS	PPS+Report+App+AMS
Hospital 3	PPS+Report	PPS+Report+Paper-based	PPS+Report+Paper-based	PPS+Report+App+AMS	PPS+Report+App+AMS
Hospital 2	PPS+Report	PPS+Report+Paper-based	PPS+Report+App+AMS	PPS+Report+App+AMS	PPS+Report+App+AMS
Hospital 1	PPS+Report	PPS+Report+Paper-based	PPS+Report+App+AMS	PPS+Report+App+AMS	PPS+Report+App+AMS
	Month 0	Month 4	Month 8	Month 12	Month 16
	Activity at month 0	Activity at month 4	Activity at month 8	Activity at month 12	Activity at month 16
	AMS survey for all sites	AMS survey*	AMS survey*	AMS survey*	AMS survey for all sites
	Pre-prescribing survey	AMS training*	AMS training*	AMS training*	Prescriber feedback survey on the App guideline**
	Introduce paper-based guideline	Introduce App guideline*	Introduce App guideline*	Introduce App guideline*	
		Prescriber feedback survey on paper-based guideline*	Prescriber feedback survey on paper-based guideline*	Prescriber feedback survey on paper-based guideline*	
			Prescriber feedback survey on the App guideline**	Prescriber feedback survey on the App guideline**	

* This activity will only be performed in a new selected paired hospital

** This activity will only be performed 4 months after introducing App guideline in each paired hospital

c.4 Contamination prevention

Although the clusters are geographically quite remote from each other, travel and communications between doctors in Laos is quite frequent. There is a possibility of contamination of the app to the reference group (however this is judged to be unlikely). The research team will record this if it occurs. Examples of how this could happen are:

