3.7 Data collection method

Open Data Kit (ODK) system will be used as the data collection tool for PPS. Outcomes will be measured by regular PPS of hospital antimicrobial prescribing in both in- and outpatients (details as below) at all six hospitals during 4 monthly visits (five visits including one baseline data collection). Data will be collected using separate electronic questionnaires for in- and outpatients.

Paper case report forms (CRF) will be used for the prescriber surveys (Appendix A9. *Pre-prescribing guideline survey*; A10. *Prescriber feedback survey on paper-based prescribing guidelines*, A11. *Prescriber feedback survey on mobile phone app prescribing guidelines* and A5. *Antimicrobial stewardship knowledge survey*) will be distributed to all doctors in each study hospital in different time periods (Figure 2).

Each data collector will be trained on the study purpose/processes and the use of the data collection instruments before starting the project. IPD and OPD PPS data will be collected in ODK on patients' characteristics and treatment status, including age, sex, body weight, wards, antimicrobial agent (s), administration, dosage, unit, diagnoses, prescribing indication and antimicrobial start date. IPD PPS data will be collected directly from hospital charts and OPD PPS data will be obtained from the scanned prescription sheets. Data on the frequency of use of the mobile app can also be downloaded from the MicroGuide App.

Basic information (age, sex, specialty, departments, graduated year) of prescribers and their prescribing behaviors will be collected via survey forms (either prescriber feedback survey or AMS survey). All complete survey forms by prescribers will be returned to study team on the same day as the survey day. All data will be entered to MACRO system.

We will only consider antibiotic costs. Name of antimicrobials, dose, dosage form, manufacturing country of antibiotics will also be collected from each pharmacy hospital.

a. Point Prevalence Survey procedures

a.1 In-patient point prevalence survey

Design – Point prevalence survey

Survey site - All in-patient wards from all 6 participating hospitals:

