All data will be entered by PI and trained research staff. All complete survey forms will be kept securely in a locked filing cabinet. Only the PI of the project and project data management team will have access to the raw data. All electronic data will be kept securely, protected by password access with automatic daily backup on the server at Lao-Oxford-Mahosot Hospital-Wellcome Trust Research Unit (LOMWRU) office and regular offsite tape backups. All scanned OPD prescription sheets will be appropriately destroyed within one month after the scanned date. Anonymized data from PPS will be fed back to the participating hospitals and Ministry of Health through a project-generated computer dashboard and reports one month after each PPS in each hospital. Data checking and cleaning will be done by the PI after each survey. Data inconsistency will be discussed with the research team immediately.

Statistical analysis

Normally distributed continuous baseline characteristics will be summarized with means and standard deviations. Skewed continuous data will be summarized using median and inter-quartile range. Categorical data will be presented as frequency and percentages. A logistic mixed effects regression model will be used to compare the proportion of antimicrobial prescriptions adherence

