measured cross-sectionally at month 0, 4, 8, 12 until month 16 after introduction of prescribing guidelines by mobile phone application versus paper-based (30). The model will compare all wedges in the intervention from month 4 to month 16 with all wedges in the reference arm from month 0 to month 12. The duration of exposure of each hospital to the reference or intervention arm will be included in the model as interaction term with the study arm in order to assess whether the duration of exposure is the effect modifier. The model will consider the correlation among the outcome's measurements from the same hospital (cluster) by adjusting for clustering in the model. Odds ratios and the corresponding confidence intervals will be obtained and reported. Tests of significance will be performed at 5% level. Analyses will be done using Stata 15.0 or higher. Likert scale analysis will be used to evaluate prescriber satisfaction with/ acceptability of paper-based compared to mobile phone app delivered antimicrobial prescribing guidelines. The satisfaction/acceptability scale will be assigned in six categories, including strongly agree=5, agree=4, neutral=3, disagree=2 and strongly disagree=1, no opinion/not use=0. Mann-Whitney test will be used to assess the differences between paper-based population and mobile phone app population. AMS knowledge level of prescribers will be assessed using questionnaires based on information in the prescribing guidelines. The overall proportion of correct answers in each time point will be compared (baseline, after paper-based guidelines (before AMS training and introduction of mobile phone app guidelines) and after AMS training and introduction of mobile phone app guidelines). Other factors such as extra AMR training program from hospital/MoH/other organizations, level of education and specialties of prescribers will also be taken into account.

Cost of antibiotic therapy will be calculated from the start date of treatment to the survey day. The unit costs for the antibiotics will be obtained from the [International Medical Product Price Guide](#).

Antibiotic defined daily dose (DDD) will be calculated using data (antibiotic agent, start date, dose and DDD of each antibiotic from www.whooc.no) from PPS in both IPD and OPD. Antimicrobial cost data from participating hospitals will also be collected each hospital pharmacy for comparison with international cost.

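### Three regional pairs are randomised, but the primary model allows for correlation within hospital only, so its interval is too narrow if adherence shifts by region from survey to survey

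*Combined protocol and SAP*

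**What the plan says.** Section 3.4 (Randomization and blinding) fixes the grouping before the draw: "Six participating hospitals have been divided into 3 pairs based on the geographical location and convenience for conducting the surveys". The pairs are north (Luang Namtha, Xiengkhuang), centre (Mahosot, Vientiane Provincial) and south (Savannakhet, Salavan). The draw is of pairs: "Three paired hospitals (LNT+XK, MS+VTP and SVK+SV) will be written on three different paper slips". The synopsis agrees that random sampling is used "to select the order (step) of interventions implementation for a group of hospitals (two hospitals per group and one group per step"). Both hospitals of a region therefore always switch to the app on the same date.

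The Statistical analysis subsection plans the primary comparison at hospital level: "A logistic mixed effects regression model will be used to compare the proportion of antimicrobial prescriptions adherence", and "The model will consider the correlation among the outcome's measurements from the same hospital (cluster) by adjusting for clustering in the model". It names an interaction of exposure duration with study arm. It names no survey (calendar period) effect, no pair or region term, no small-sample correction and no randomisation-based test. Section 3.3 counts the sample size as six hospitals.

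**The concern.** The unit randomised (three pairs) is not the unit whose correlation the model allows for (six hospitals), and the plan does not say so. If something moves adherence in one region between surveys, such as a local outbreak, a drug supply problem or another programme, both hospitals of the pair move together. They also share a switching date, so the model reads the shift as part of the app effect and counts it as two independent observations. The standard error does not reflect that, and the confidence interval and p-value would look firmer than the design supports.

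The Risks section gives one possible source. Another antimicrobial-resistance programme, planned to start with the trial and run for 18 months, covers both northern hospitals, one southern and neither central hospital. The plan is to record its trainings and possibly to compare knowledge levels by programme status. Adjusting the adherence model for it is not mentioned.

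**Working it through.** **The plan's own figure.** Section 3.3 states 80% power for 30% adherence, a 15% difference, ICC 0.05 and six hospitals. It gives no number of prescriptions per hospital-survey (m), so the figure can only be back-solved. With the Hussey-Hughes stepped-wedge variance and 30% to 45%, 80% needs m of 36 to 45 if the hospital effect is constant over time. It needs m of 57 to 81 if the cluster autocorrelation is 0.8. The figure is attainable, but it assumes six independent hospitals.

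**Possible allocations.** Three slips: 3! = 6 orders, smallest randomisation p = 1/6 = 0.167. Hospitals drawn singly, two per date: 6!/(2!2!2!) = 90 allocations, smallest p = 1/90 = 0.011.

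**Inputs for the standard error.**
- From the documents: ICC 0.05; six hospitals, two per step; surveys at months 4, 8, 12 and 16, with 0, 2, 4 and 6 hospitals on the app (Figure 2).
- Assumed: mean adherence 37.5% (midpoint of 30% and 45%); m = 45 or 150; region-by-survey SD s = 3 or 5 percentage points; linear model with survey effects and a hospital random intercept; two-sided normal test.

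**Standard error the model reports.** Total variance is 0.375 × 0.625 = 0.2344. Between-hospital variance is τ² = 0.05 × 0.2344 = 0.01172. Cell variance is σ² = 0.95 × 0.2344/m, which is 0.00495 at m = 45 and 0.00148 at m = 150.

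Var = Nσ²(σ² + Tτ²) / [(NU − W)σ² + (U² + NTU − TW − NV)τ²]

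Here N = 6, T = 4, U = 12 (hospital-surveys on the app), W = 0 + 4 + 16 + 36 = 56 and V = 2(9 + 4 + 1) = 28. So NU − W = 16, and U² + NTU − TW − NV = 144 + 288 − 224 − 168 = 40.
- m = 45: 6 × 0.00495 × 0.0518 / (0.0792 + 0.4688) = 0.00281, SE 5.30 points.
- m = 150: 6 × 0.00148 × 0.0484 / (0.0238 + 0.4688) = 0.00087, SE 2.96 points.

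**Actual standard error.** A shift shared by a pair at one survey adds k·s², where k is the sum over pair-surveys of (the two hospitals' estimator weights added together)². From the weights, k = 1.08 at m = 45. For s = 3: 5.30² + 1.08 × 9 = 28.09 + 9.72 = 37.81, SE 6.15. For single draws, k is averaged over the 90 allocations and is smaller.

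**Type I error** = 2Φ(−1.96 × model SE / actual SE). For the first row: 1.96 × 5.30/6.15 = 1.69, giving 9%.

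| m | s (points) | Model SE | Actual SE, pairs | Type I, pairs | Actual SE, single draws | Type I, single draws |
|---|---|---|---|---|---|---|
| 45 | 0 | 5.30 | 5.30 | 5% | 5.30 | 5% |
| 45 | 3 | 5.30 | 6.15 | 9% | 5.65 | 7% |
| 45 | 5 | 5.30 | 7.42 | 16% | 6.23 | 10% |
| 150 | 3 | 2.96 | 4.38 | 19% | 3.59 | 11% |
| 150 | 5 | 2.96 | 6.14 | 35% | 4.51 | 19% |

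Using five surveys, or 30% adherence, moves the error rates by about 2 points at most.

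**Check with a logistic model.** Simulation under no effect (30% adherence, hospital intercept, period effects, 2,000 runs per setting) gives 5.4% (m = 45) and 5.8% (m = 100) when there is no period-specific variation. When that variation is 10% of the between-hospital variance and shared within the pair, the rates are 8.8% and 13.2%; at 20% they are 15.1% and 21.1%. When it is independent by hospital, they are 8.0% and 10.9% (at 10%), and 10.4% and 13.7% (at 20%).

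**Pairing alone.** A cell-mean model that already allows for hospital-by-survey noise was run with shared variation of 10%, 20% and 40%. It gives 6.7%, 8.9% and 11.7% (m = 50), and 8.6%, 11.4% and 14.9% (m = 100). A pair-level analysis stays at 4.7% to 5.2%.

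**The case against.** Four stronger readings are tempting, and the documents support none of them.

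- **Region is confounded with start date, so the estimate is biased.** Every hospital contributes both reference and app surveys, and stable regional differences fall into the hospital effect. A nationwide season would be absorbed by survey effects, if these are fitted. The other programme does not follow the pairs exactly (Salavan has it, Savannakhet does not). A constant programme effect would also be absorbed; only one that builds over time would act as region-by-time variation.
- **The p-value overstates the evidence in any event.** It does so only if there is variation between surveys that the model omits. Without it, error stays at 5% to 6%. The single-draw columns also exceed 5%, because a hospital intercept alone has no cluster-by-survey term. Part of the inflation is therefore not due to pairing.
- **Mixing regions within a step would cost nothing.** Outcomes are measured "at all six hospitals during 4 monthly visits", but a trained local doctor may run the surveys, whereas the principal investigator installs the app and leads both training sessions. Section 3.1 gives delivery by one travelling team as a reason for the staged design. Extra travel cannot be ruled out. Contamination is covered by "however this is judged to be unlikely", but that judgement was made for a plan in which neighbours switch together, and c.4 also notes that doctors travel often.
- **The 1/6 floor invalidates the planned test.** No randomisation test is planned. The floor shows only that significance rests on the model.

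It is also fair to say that the analysis text does not spell out the random-effects structure, that the methods paper it cites is not available here, and that the calculation is linear and omits the exposure-duration interaction. The percentages are illustrations, not this trial's error rate. What stands is that nothing in the text makes the analysis respect the pair that was drawn.

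**Conclusion.** The mismatch is real, and its effect is conditional. Three pairs are randomised, with six possible orders, while the primary model allows for correlation within hospital only. If adherence varies by region from survey to survey, the confidence interval for the app effect is too narrow. Under the assumed SD of 3 to 5 points and 45 to 150 prescriptions per hospital-survey, type I error is about 9% to 35% against a nominal 5%. About 7% to 19% would remain if hospitals had been drawn singly. With no such variation the model is close to its nominal level. Whatever the size, six orders cannot give a randomisation p-value below 0.167, so any significant result depends on the model's independence assumption. Neither the prescription counts nor the SDs are in the documents.

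**What to change.** 1. In section 3.4, name the regional pair as the unit of randomisation and state that there are six possible orders.
2. In the Statistical analysis subsection, include survey effects and allow for variation by survey at both hospital and pair level, with a small-sample correction. Pre-specify this at least as a sensitivity analysis reported beside the primary model.
3. State that statistical significance is model-dependent, because the randomisation alone cannot reach 5%.

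**Cost.** The text and programming are minor. The interval will be wider, and a pair-by-survey variance is poorly estimated from three pairs. Making a pair-level analysis primary would be expensive. At the m that gives 80% by the normal test, power is about 57% for a t-test on six clusters (4 df) and about 17% on three pairs (1 df). That is why a sensitivity analysis is the minimum asked for.

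**Option before the draw only.** Six slips, two hospitals per date, would give 90 allocations. This does not by itself restore 5% error, so the extra variance terms are still needed. It must also be weighed against the principal investigator's travel and contamination between neighbouring hospitals in different phases.
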